4.7.1 Tivozanib Hydrochloride Dose Modification

Clinical judgment will be used to determine appropriate management of the subject experiencing any adverse event (AE). The suggested criteria for dose modification for tivozanib hydrochloride drug-related AEs (excluding hypertension) are summarized in the table below.

Drug-Related	Action Taken	Subsequent Dosing Modification		
Adverse Events				
(excluding				
Hypertension ¹)				
Grade 1	No dose interruption, or reduction	None required; Dosing may continue		
	required; adverse event	at the same dose		
	management is at the discretion of			
	the Investigator			
Grade 2 No dose interruption, or reduction		None required; Dosing may continue		
	required; adverse event	at the same dose		
	management is at the discretion of			
	the Investigator			
Grade 3 ²	Interrupt dosing ³ until toxicity	Dosing may resume at same dose or		
	resolves to \leq grade 1.	reduced dose at the discretion of the		
		Investigator (see below for dose		
		reduction guidelines).		
Grade 4	Interrupt dosing until toxicity	Dosing may resume at same dose or		
	resolves to \leq grade 1.	reduced dose at the discretion of the		
	_	investigator (see below for dose		
		reduction guidelines).		

Tivozanib Hydrochloride Dose Modification Guidelines for Drug-Related Adverse Events

- 1. Hypertension must be treated as described in Appendix C prior to any dose modification
- 2. Referring to toxicity that persists despite appropriate medical care.
- 3. Tivozanib may be interrupted for up to 2 weeks. If a subject is able to resume treatment after an interruption of ≤ 2 weeks, missed doses will not be made up (i.e. the cycle duration will remain unchanged). If any drug related toxicity results in interruption of >2 weeks, the subject should be discontinued from study treatment unless there is clear benefit.

Patients should be followed for assessment of the toxicities until the AEs resolve or are deemed irreversible. The maximum delay of drug administration by the treating investigator or the patients' own decision for any reason, including toxicities, is 2 weeks. If the drug is withheld for more than 2 continuous weeks due to a treatment-related toxicity that does not resolve, the patient will be withdrawn from study treatment. The exception is HTN, which must first be treated as described in Appendix C prior to any dose modification.

Patients will be withdrawn from the study if they fail to recover to grade ≤ 1 or tolerable grade 2 (or within 1 grade of starting values for pre-existing laboratory abnormalities) from a treatment-related toxicity within 2 weeks OR if they experience agent related adverse events requiring dose modification despite previous dose reductions (i.e. would require a 2nd dose reduction) unless the investigator agrees that the subject should remain in the study because of evidence that the patient is/may continue deriving benefit from continuing study treatment. The appropriate reduced dose will be determined after discussion with the principal investigator and approval of the Data Monitoring Committee. Patients requiring dose reductions should not have the dose re-escalated with subsequent treatments. If treatment was interrupted for < 1 week, the patient will resume dosing on the current treatment cycle. If treatment was interrupted for ≥ 1 week, the patient will start a new cycle of treatment.

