4.7.2 Tivozanib Hydrochloride Dose Reduction

Dose reductions of tivozanib hydrochloride to 1.0 mg/day will be allowed for subjects with \geq Grade 3 drug-related adverse events. The exception is hypertension, which must be treated with anti-hypertensive drugs prior to dose reduction. Once a subject's dose of tivozanib hydrochloride is reduced, it may not be re-escalated through the remainder of the subject's participation in the study. If a subject is unable to tolerate a reduced dose due to toxicities thought to be related to treatment, treatment should be discontinued.

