6.1.7 Protocol Dose

The following dosage strengths will be made available:

1.5 mg

1.0 mg

The amount of study drug dispensed to the subject at the beginning of each dosing cycle will be sufficient to allow for 3 weeks (21 days) of consecutive once-daily dosing of tivozanib hydrochloride. Dosing compliance will be monitored at each clinic visit.

- 6.1.8 Route of Administration Tivozanib hydrochloride is formulated for oral administration as a white opaque number 4 gelatin capsule.
- 6.1.9 Availability Provided at free of charge by AVEO Pharmaceuticals, Inc.

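### The dose-reduction rules conflict on when a reduction applies, who authorises it, and what follows if the reduced dose is not tolerated

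*Combined protocol and SAP*

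**What the plan says.** Four places in the protocol govern what happens after a drug-related toxicity of grade 3 or 4 (hypertension has separate handling in Appendix C and is left aside here).

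- **Section 4.2.4** interrupts treatment until the toxicity is grade 2 or less, states that a reduction is made, and discontinues tivozanib if there is no such recovery or if grade 3 or 4 recurs.
- **Section 4.7.1, table**, holds dosing to grade 1 or less. On restarting it reads "Dosing may resume at same dose or" and continues "reduced dose at the discretion of the" "Investigator (see below for dose", pointing to the reduction guidelines that follow.
- **Section 4.7.1, closing paragraph**, withdraws patients who do not recover within 2 weeks, and those with events "requiring dose modification despite previous dose reductions (i.e. would require a 2nd dose reduction) unless the investigator agrees" that the patient should remain because of benefit. The next sentence is: "The appropriate reduced dose will be determined after discussion with the principal investigator and approval of the Data Monitoring Committee".
- **Section 4.7.2** reads "Dose reductions of tivozanib hydrochloride to 1.0 mg/day will be allowed for subjects with" drug-related events of grade 3 or higher, and adds: "If a subject is unable to tolerate a reduced dose due to toxicities thought to be related to treatment, treatment should be discontinued".

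On supply, Section 6.1.7 ("The following dosage strengths will be made available") lists 1.5 mg and 1.0 mg only, and Section 4.2.3 limits intake to one capsule a day. Section 4.7.1 also sets a 2-week maximum delay.

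**The concern.** A site has to know, for a given patient, whether it must reduce, at what toxicity grade it may restart, whether it may restart on its own authority, and whether a patient who fails on the reduced dose may continue. The four places give different answers, and the approval sentence carries neither a scope nor a turnaround time.

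At stake is consistent and safe treatment. The trial runs at several Northwestern sites (Section 3). Two sites could each follow the protocol as they read it and still differ in the dose a patient resumes, the grade at which she resumes, and whether she stays on drug. Dose received and time on drug may bear on response and progression-free survival, and Section 8 tabulates weeks of treatment. The documents give no basis for a size or direction of any such effect.

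**Working it through.** There is no figure to reproduce, because the point depends on no error rate, power, effect size or event count. The check sets the texts side by side.

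| Question | 4.2.4 | 4.7.1 table | 4.7.1 closing paragraph | 4.7.2 |
|---|---|---|---|---|
| Reduce after drug-related grade 3 or 4? | Yes, always | Investigator's choice | Not stated | Permitted |
| Recovery grade | 2 or less to resume | 1 or less to resume | Withdraw if not 1 or less, or tolerable 2, within 2 weeks | Not stated |
| Who authorises? | Not stated | Investigator | Discussion with the principal investigator and committee approval | Not stated |
| Reduced level | Not stated | Deferred to guidelines below | To be determined | 1.0 mg/day |
| Reduced dose not tolerated | Discontinue on recurrent grade 3 or 4 | Not stated | Withdraw unless the investigator sees benefit | Discontinue |

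**Step 1: the approval sentence read broadly (every reduction).** The sentence after it, which bars re-escalation, applies to all patients with reductions, and this favours the broad reading. Committee approval is then required for a step that the table gives to the investigator and that 4.7.2 permits without approval. A site cannot tell whether dosing may resume before approval.

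**Step 2: the approval sentence read narrowly (only the exception patients just before it).** A first reduction then follows the table and 4.7.2 with no committee step. But the same paragraph lets a patient who would need a second reduction stay on treatment, with a dose still to be determined. Section 4.7.2 discontinues a patient who cannot tolerate a reduced dose, and 4.2.4 discontinues on recurrent grade 3 or 4; neither has a benefit exception. A patient already on 1.0 mg has no lower strength available. Section 6.1.6 mentions stability data for strengths from 0.5 mg, but 6.1.7 does not list 0.5 mg as supplied. For her, the approval step has no lower dose to approve.

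**Step 3: independent of either reading.** Section 4.2.4 and the table disagree on whether a reduction is made and on the grade for resuming.

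**Step 4: timing.** The protocol gives no turnaround for dose approvals. Elsewhere the committee works by meeting: Section 9.3.3.1 has it review serious adverse events at its next one. Section 4.7.1 does not say how an approval wait relates to the 2-week maximum.

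**Step 5: rough size, by assumption only.** Section 1.2.3 reports reductions for adverse events in 12% of tivozanib patients in the phase III renal-cancer trial: 0.12 × 30 = 3.6 patients. As a loose reference for how many might meet the Step 3 conflict, two studies that used 1.5 mg/day throughout report at least one event of grade 3 or higher in 38.0% and 48.6%: 0.380 × 30 = 11.4 and 0.486 × 30 = 14.6. Those rates include hypertension and unrelated events, so they overstate the relevant group within those studies. Two smaller studies that included other doses were higher (12 of 17 and 31 of 41).

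**The case against.** The best defence is that most of the text fits together. The table leaves only the choice between the same and a reduced dose to the investigator and defers the level to the guidelines below; 4.7.2 supplies that level and is worded as permission, so the two agree. The approval sentence follows directly on the exception for patients kept on treatment, and read in place it can concern them alone. Section 4.7.1 also describes its table as suggested criteria subject to clinical judgement.

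Much of this stands, and it rules out three stronger readings that a reader might infer.

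- **Three competing dose levels.** The documents do not support this: only 1.0 mg/day is named.
- **An unknown dose at first reduction.** Not supported either: 1.0 mg is the only lower strength supplied, at one capsule a day. The open questions there are authorisation and waiting.
- **Waiting for the committee would push recovered patients off treatment.** No turnaround is given. The withdrawal sentence concerns toxicity that has not resolved, and footnote 3 of the table has an exception for clear benefit. The cap on delay for any reason gives some support, but it is worded for delays decided by the investigator or patient.

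What the defence does not remove is Step 2, which is the price of the narrow reading, and Step 3, where 4.2.4 is worded as mandatory and the table is not.

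**Conclusion.** The concern holds as an inconsistency in authorisation, in when a reduction applies, in the recovery grade, and in what follows a reduced dose that is not tolerated. No reading of the approval sentence makes Sections 4.2.4, 4.7.1 and 4.7.2 consistent. It should be corrected, because the rules decide who stays on drug and on whose authority.

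The size is uncertain. The 3.6 of 30 rests on carrying a renal-cancer rate over to this population. If the approval sentence covers only exception patients, the number it affects is not 3.6, and the documents give no rate for that group. The two-stage design, its 5% and 20% response rates and its decision limits are untouched.

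**What to change.** Reconcile Sections 4.2.4, 4.7.1 (table and closing paragraph) and 4.7.2 so that they give one consistent statement of:

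- when a reduction applies after drug-related grade 3 or 4 toxicity;
- the recovery grade for resuming;
- who authorises a reduction;
- which cases need committee approval, and how that approval relates to the 2-week maximum delay;
- what happens when a reduced dose is not tolerated, consistent with the strengths in 6.1.7 and the one-capsule rule in 4.2.3.

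This review does not say which dose or rule is right; that is for the sponsor-investigator. The cost is protocol wording, carried through the usual amendment approval. Sample size, endpoints and analysis do not change.

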4.7.2 Tivozanib Hydrochloride Dose Reduction

Dose reductions of tivozanib hydrochloride to 1.0 mg/day will be allowed for subjects with \geq Grade 3 drug-related adverse events. The exception is hypertension, which must be treated with anti-hypertensive drugs prior to dose reduction. Once a subject's dose of tivozanib hydrochloride is reduced, it may not be re-escalated through the remainder of the subject's participation in the study. If a subject is unable to tolerate a reduced dose due to toxicities thought to be related to treatment, treatment should be discontinued.

5 RESPONSE ASSESSMENT

The measures used to determine the objective overall response rate will be those that are already in place for determining treatment efficacy. Specifically, we will utilize physical exam findings performed at the commencement of each 4-week cycle of treatment during a clinician visit. Additionally, serum CA-125 levels will be checked at the commencement of each 4 week cycle of treatment to determine disease status. If otherwise indicated by disease state, we will obtain CT scan or MRI or chest x-ray and utilize index target lesions and RECIST 1.1 criteria to

determine treatment efficacy and response rate.

5.1 Antitumor Effect – Solid Tumors

Response and progression will be evaluated in this study using the international criteria proposed by the revised Response Evaluation Criteria in Solid Tumors (RECIST) guideline (version 1.1) [16]. Changes in the largest diameter (unidimensional measurement) of the tumor lesions and the shortest diameter in the case of malignant lymph nodes are used in the RECIST criteria.

5.2 Disease Parameters

5.2.1 Measurable disease

Measurable lesions are defined as those that can be accurately measured in at least one dimension (longest diameter to be recorded) as >10 mm with CT scan, as >20 mm by chest x-ray, or >10 mm with calipers by clinical exam. All tumor measurements must be recorded in millimeters (or decimal fractions of centimeters). Lymph nodes are considered measurable in RECIST 1.1 if their short diameter exceeds 15 mm. Lymph nodes are considered normal if they have a short axis of less than 10 mm; this applies to determination of response as well.

Lesions that are previously irradiated must show clear evidence of progression over a minimum of 3 months to include as measurable. This period of time is used to discount tumor edema in an irradiated field as a false sign of disease progression.

5.2.2 Non-measurable disease

All other lesions (or sites of disease), including small lesions (longest diameter <10 mm or pathological lymph nodes with >10 to <15 mm short axis), are considered non-measurable disease. Bone lesions, leptomeningeal disease, ascites, pleural/pericardial effusions, lymphangitis cutis/pulmonis, inflammatory breast disease, abdominal masses (specifically abdominal masses that cannot be followed by CT or MRI), and cystic lesions are all non-measurable.

Note: Bone lesions: Lytic bone lesions or mixed lytic-blastic lesions, with identifiable soft tissue components, that can be evaluated by CT or MRI can be considered as measurable lesions if the soft tissue component meets the definition of measurability described above. Blastic bone lesions are non-measurable.

Cystic lesions that meet the criteria for radiographically defined simple cysts should not be considered as malignant lesions (neither measurable nor non- measurable) since they are, by definition, simple cysts. 'Cystic lesions' thought to represent cystic metastases can be considered as measurable lesions, if they meet the definition of measurability described above. However, if non-cystic lesions are present in the same patient, these are preferred for selection as target lesions.

5.2.3 Target lesions

All measurable lesions up to a maximum of 2 lesions per organ and 5 lesions in total, representative of all involved organs, should be identified as **target lesions** and recorded and measured at baseline. Target lesions should be selected on the basis of their size (lesions with the longest diameter) and their suitability for accurate repeated measurements (either by imaging techniques or clinically). A sum of the longest diameter (LD) for all target lesions will be calculated and reported as the baseline sum LD. The baseline sum LD will be used as reference by which to characterize the objective tumor response.

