3.1 Inclusion Criteria

Each patient must meet all of the following inclusion criteria to be enrolled in the study:

- 3.1.1 Patients must have recurrent or persistent, platinum resistant or refractory epithelial ovarian, fallopian tube or primary peritoneal carcinoma. Platinum-resistant disease is defined as a recurrence within 6 months of completing platinum-based chemotherapy.
- 3.1.2 Patients must have measurable disease or non-measurable (detectable) disease:
 - Measurable disease is defined as at least one lesion that can be accurately measured in at least one dimension (longest diameter to be recorded). Each lesion must be greater than or equal to 10 mm when measured by CT, MRI or by clinical exam; or greater than or equal to 20 mm when measured by chest x-ray. Lymph nodes must be greater than or equal to 15 mm in short axis when measured by CT or MRI.

- Non-measurable (detectable) disease in a patient is defined in this protocol as one who does not have measurable disease based on RECIST criteria but does have a CA-125 greater than or equal to two times the upper normal limit within the last 60 days (confirmatory at baseline) and at least one of the following conditions:
 - Ascites and/or pleural effusion attributed to tumor
 - Hypermetabolic lesions on PET Scan
- 3.1.3 Patients with measurable disease must have at least one target lesion as defined by RECIST 1.1 to be used to assess response on this protocol.
- 3.1.4 Patients must have an ECOG Performance Status of 0, 1, or 2.
- 3.1.5 Patients must have had one prior taxane and platinum-based chemotherapeutic regimen for management of primary disease containing carboplatin, cisplatin, or another organoplatinum compound. This initial treatment may have included intraperitoneal therapy, consolidation, non-cytotoxic (biologic/targeted agents) or extended therapy administered after surgical or non-surgical assessment. There is no maximum number of prior regimens.

Note: Use of bevacizumab as maintenance therapy after initial adjuvant platinumbased chemotherapy is allowed so long as platinum-resistant recurrence occurred subsequent to a separate platinum-based regimen AND more than 6 months after completion of bevacizumab maintenance.

- 3.1.6 Patients must have signed an approved informed consent and authorization permitting the release of personal health information.
- 3.1.7 Patients must be willing and able to complete all study procedures.

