5.3 Methods for Evaluation of Measurable Disease

All measurements should be taken and recorded in metric notation using a ruler or calipers. All baseline evaluations should be performed as closely as possible to the beginning of treatment and never more than 28 days before the beginning of the treatment.

The same method of assessment and the same technique should be used to characterize each identified and reported lesion at baseline and during follow-up. Imaging-based evaluation is preferred to evaluation by clinical examination when both methods have been used to assess the antitumor effect of a treatment.

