5.4.1 Evaluation of Target Lesions

Complete Response (CR): Disappearance of all target lesions. Any pathological lymph nodes (whether target or non-target) must have reduction in short axis to <10 mm.

Partial Response (PR): At least a 30% decrease in the sum of the diameters of target lesions, taking as reference the baseline sum diameters.

Progressive Disease (PD): At least a 20% increase in the sum of the diameters of target lesions, taking as reference the smallest sum on study (this includes the

baseline sum if that is the smallest on study). In addition to the relative increase of 20%, the sum must also demonstrate an absolute increase of at least 5 mm. (Note: the appearance of one or more new lesions is also considered progressions).

Stable Disease (SD): Neither sufficient shrinkage to qualify for PR nor sufficient increase to qualify for PD, taking as reference the smallest sum diameters while on study.

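### Section 5.2.3 builds the baseline tumour sum from the longest diameter of every target lesion, which conflicts with the short-axis rule for lymph nodes stated elsewhere in the protocol

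*Combined protocol and SAP*

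**What the plan says.** Section 5.2.3 gives the only definition of the baseline sum: "A sum of the longest diameter (LD) for all target lesions will be calculated and reported as the baseline sum LD". The next sentence gives it its role: "The baseline sum LD will be used as reference by which to characterize the objective tumor response".

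Other sections treat nodes differently:

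- Section 5.1, which adopts RECIST 1.1 for response and progression, says that changes in the largest diameter of tumour lesions and "the shortest diameter in the case of malignant lymph nodes are used in the RECIST criteria".
- Section 3.1 (criterion 3.1.2) qualifies nodes by short axis: "Lymph nodes must be greater than or equal to 15 mm in short axis when measured by CT or MRI". Section 5.2.1 does the same: "Lymph nodes are considered measurable in RECIST 1.1 if their short diameter exceeds 15 mm". Nodes can therefore be target lesions.
- The complete-response rule in 5.4.1 says that pathological nodes, target or non-target, "must have reduction in short axis to <10 mm".
- The partial-response rule in 5.4.1 names no axis: "At least a 30% decrease in the sum of the diameters of target lesions, taking as reference the baseline sum diameters".

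Section 5.3 adds a general consistency rule: "The same method of assessment and the same technique should be used to characterize each identified and reported lesion at baseline and during follow-up".

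**The concern.** For a nodal target, the reference sum and the criteria applied to it are defined on different axes. Nowhere does the protocol put the nodal short axis into the baseline sum. A site has two ways to follow the text, and each has a fault. Longest diameter at every visit departs from 5.1. Longest diameter at baseline (5.2.3) with short axis at follow-up (5.1) compares two different measurements of the same node.

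The stake is the primary endpoint. Response rate is judged by a two-stage rule in section 8: stop if none of the first 10 patients responds, otherwise reject the null with 4 or more responses among 30. With thresholds this low, one or two misclassified patients could change the conclusion.

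**Working it through.** **1. Inputs.** Baseline sum and its role: 5.2.3. Nodal axis: 5.1, 3.1, 5.2.1 and the complete-response rule in 5.4.1. Partial response: a fall of at least 30% from the baseline sum (5.4.1). Progression: a rise of at least 20% and at least 5 mm from the smallest sum on study (5.4.1). Decision rule: section 8. Node sizes below are illustrative (longest diameter x short axis); the documents give none.

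**2. Longest diameter at every visit.** A node goes from 25 x 16 mm to 20 x 11 mm and is the only target.

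- Short axis: 11/16 - 1 = -31%, partial response.
- Longest diameter: 20/25 - 1 = -20%, stable disease.

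Here a response under 5.1 is missed.

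**3. Longest diameter at baseline, short axis at follow-up.** For unchanged lesions,

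change = sum over nodes of (short axis - longest diameter) / baseline sum of longest diameters.

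With a node as the only target, the apparent fall reaches 30% when short axis / longest diameter is 0.70 or less.

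| Unchanged node | Apparent change | Scored as |
|---|---|---|
| 20 x 16 mm | 16/20 - 1 = -20% | stable |
| 22 x 16 mm | 16/22 - 1 = -27% | stable |
| 25 x 16 mm | 16/25 - 1 = -36% | partial response |
| 30 x 20 mm | 20/30 - 1 = -33% | partial response |

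Other target lesions dilute the artefact. For an unchanged 30 x 18 mm node plus an unchanged non-nodal lesion of L mm, the change is -12/(30 + L). At L = 20 this is -24%, stable disease; it reaches -30% only if L is 10 mm or less. The node must therefore dominate the sum.

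The same mixture can hide growth. A node whose baseline is 30 x 18 mm and whose short axis grows to 24 mm has risen by 24/18 - 1 = +33% and by 6 mm, which is progression. Against a 30 mm baseline it reads 24/30 - 1 = -20%. This masks growth only up to the first follow-up scan, because from then on the smallest sum on study is itself a short-axis sum.

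Section 7.1, footnote 11, requires confirmation of responses at 4 weeks or later. That does not remove a false partial response of this kind, because the axis mismatch repeats at the confirming scan.

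**4. How sensitive the decision rule is.** With response probability p, the chance of rejecting the null is

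sum over x = 1 to 10 of P[Bin(10, p) = x] x P[Bin(20, p) >= 4 - x].

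The stated design is first reproduced: 5.13% at p = 0.05 and 81.4% at p = 0.20, against the stated 5% and 80%.

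Now suppose, **purely as an illustration**, that a share q of true non-responders were falsely scored as partial responses. Then p = 0.05 + 0.95q:

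| q (assumed) | p | Chance of rejecting at a true 5% rate |
|---|---|---|
| 0 | 0.0500 | 5.1% |
| 1% | 0.0595 | 8.5% |
| 2% | 0.0690 | 12.7% |
| 3% | 0.0785 | 17.7% |

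No value of q can be taken from the documents.

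**5. After the fix.** With the short axis at both times, the unchanged 25 x 16 mm node goes from 16 to 16 mm, a change of 0%, and is stable. The shrinking node in step 2 is correctly scored at -31%.

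**The case against.** The strongest reply is that no section tells a site to mix axes. Section 5.1 speaks of changes in the shortest diameter of nodes, and a change needs that diameter at both times. Section 5.3 asks for the same method and technique at baseline and follow-up. The partial-response rule names no axis and refers to a baseline sum of diameters, so 5.2.3 looks like the one outlying phrase in a text that otherwise follows RECIST 1.1. With either axis used consistently, an unchanged node reads 0%.

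Most of this stands. A reader might infer that the plan scores unchanged nodes as responders. The documents do not support that: it needs the mixed reading, a short/long ratio of 0.70 or less, and a node that dominates the target sum. Nor can the error reach every patient, since section 3.1 admits patients without measurable disease on CA-125 together with effusion or PET findings.

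What does not stand is that the other sections settle the matter. Section 5.3 names no axis, and 5.2.3 and 5.1 point opposite ways on which one to use. Section 5.2.3 is the specific operating instruction for the sum, and section 11.7 requires the study to be run as the protocol describes. Consistent use of the longest diameter removes the false response in an unchanged node but leaves the misclassification shown in step 2.

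**Conclusion.** Section 5.2.3 is wrong as written. It sets the response reference on the longest diameter of all target lesions, against the nodal short-axis rule in 5.1 and the matching rules in 3.1, 5.2.1 and the complete-response rule in 5.4.1. Confidence in the contradiction is high.

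Confidence in the size of its effect is low. Longest diameter throughout can miss nodal responses; the mixed reading can create them or hide early growth. The number of patients with nodal targets, and how their sums were actually formed, are not given, so the net direction is unknown. A reader might take 17.7%, or the range from 8.5% to 17.7%, as the trial's true false-positive rate. It is not: it rests on an assumed 1% to 3% of non-responders being falsely scored, and shows only that a rule needing 4 responses in 30 tolerates little misclassification.

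**What to change.** In section 5.2.3, redefine the baseline sum as *the sum of diameters (longest diameter for non-nodal lesions, short axis for nodal lesions), using the same axis at baseline and every follow-up*. Replace the term for the longest-diameter baseline sum with *baseline sum of diameters* in both places where 5.2.3 uses it, so that it matches 5.4.1.

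Before the primary analysis, identify patients with nodal target lesions, check which axis was recorded at each visit, and recompute their sums from existing scans where needed.

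Cost: a one-sentence amendment with the matching change of term, and a re-check of the forms of at most 30 patients. No new scans are required.
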